## 5.4 PARTICIPANT WITHDRAWAL OR TERMINATION

### 5.4.1 REASONS FOR WITHDRAWAL OR TERMINATION

Participants are free to withdraw from participation in the study at any time upon request. An investigator may terminate participation in the study if any clinical adverse event (AE), laboratory abnormality, new pregnancy, or other medical condition or situation occurs such that continued

participation in the study would not be in the best interest of the participant. Though highly unlikely, other circumstances under which a participant would be withdrawn without her consent include: (1) obviously not following study instructions (note: we will carefully track the number of participants who do not or cannot follow instructions as this is critical for feasibility and the design of the fully powered trial) or (2) behaving in a way that is verbally or physically abusive towards research staff. Those who experience early withdrawal will receive prorated payment based on the number of sessions they completed.

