**Objectives:**

- ***Primary Objective:***  
The goal of this study is to determine the feasibility of a human observational study of orally administered *Cannabis* use among cancer patients, towards developing feasibility/pilot data in support of an R01 grant application to the National Cancer Institute. The primary objective will be to enroll 30 patients and demonstrate reasonable compliance with study procedures within fifty-four months of active recruiting.

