**Endpoint:**

  - ***Recruitment Outcomes:***  
Number of interested patients who contact the research team  
Number of eligible potential participants  
Number of enrolled eligible participants  
Number of study assessments completed by enrolled participants  
Number of participants who complete the study

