#### **5.4.2 HANDLING OF PARTICIPANT WITHDRAWALS OR TERMINATION**

All procedures in this study are completely voluntary, and participants may withdraw their consent to participate at any point. Attempts will be made to understand why participants withdraw, as this is important for a feasibility trial, but even in that case giving investigators information concerning withdrawal is voluntary. Termination of participant by investigators, as described above, will also be tracked in case there are procedures that are not feasible for cancer patients to follow. Again, this is critical for a feasibility trial. Once participants withdraw or are terminated, there will be no attempt to follow up with or further engage with the participant.

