### 10.3 DESCRIPTION OF STATISTICAL METHODS

#### 10.3.1 ADHERENCE AND RETENTION ANALYSES

This feasibility study has an 80% retention goal for reasonable compliance with study procedures by enrolled study participants. Reasonable compliance is defined as 75% completion of study assessments. Adherence is not applicable to this observational study design.

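### Withdrawing participants for not following study instructions, then ending contact, lets staff action cut off the compliance and completion the study is meant to measure

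*Combined protocol and SAP*

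**What the plan says.** The Synopsis gives the primary objective as to "enroll 30 patients and demonstrate reasonable compliance with study procedures within fifty-four months of active recruiting", and section 3 repeats the compliance element. The Synopsis endpoints include "Number of study assessments completed by enrolled participants" and the number of participants who complete the study. Section 10.3.1 sets an 80% goal among enrolled participants and adds: "Reasonable compliance is defined as 75% completion of study assessments".

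Section 5.4.1 first lists safety-type grounds on which an investigator may end participation. It then continues: "Though highly unlikely, other circumstances under which a participant would be withdrawn without her consent include". The first circumstance listed is "1) obviously not following study instructions (note: we will carefully track the number of participants who do not or cannot follow instructions"; the second is abusive behaviour towards staff. The note in the first circumstance explains that the tracking matters for feasibility and for designing the larger trial. No threshold or decision-maker is given for *obviously*.

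Section 5.4.2 says: "Termination of participant by investigators, as described above, will also be tracked in case there are procedures that are not feasible" for this patient group. It then says: "Once participants withdraw or are terminated, there will be no attempt to follow up with or further engage with the participant".

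**The concern.** The trigger for removal is close to the behaviour being measured. Use of the product is ad libitum and staff give no dosing directions (sections 4.1, 6.1.3 and 7.3.3). The instructions a participant can fail to follow are therefore mainly study procedures: attending the remote sessions, doing the timed assessments and sending the product photograph. Whether cancer patients can manage these is the question the study asks, and section 5.3.4 itself warns that the assessments may prove too taxing.

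A patient who struggles at one point might still complete most of the schedule. Once removed, that patient cannot, because contact ends. The recorded result then reflects the removal and not what the patient could do. At stake are the compliance criterion, the completer count, and knowledge of how far struggling patients can get, which the design of the larger trial needs.

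**Working it through.** The plan has no power or precision calculation to reproduce. The 80% and 75% are set goals, and section 10.4 rests N = 30 on judgement.

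**1. The bar.** N = 30 (section 10.4) and goal 80% of enrolled (section 10.3.1): 0.80 × 30 = 24. Six failures are allowed.

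**2. Distance from the bar.** Section 2.3.1 expects attrition of 20-25%. That leaves 30 × 0.80 = 24 to 30 × 0.75 = 22.5 participants, at or just below the bar. This treats attrition as a stand-in for falling short of 75%, which is an assumption.

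**3. What removal leaves.** Table 7.1 lists 11, 9, 3, 3 and 9 measures at T00, Ta1, Tb1, Tc1 and M1, a total of 35. The protocol does not define the unit for 75%, so two units are shown.

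| Removed after | Time points done | Measures done | Meets 75%? |
|---|---|---|---|
| T00 | 1/5 = 20% | 11/35 = 31.4% | No on either |
| Ta1 | 2/5 = 40% | 20/35 = 57.1% | No on either |
| Tb1 | 3/5 = 60% | 23/35 = 65.7% | No on either |
| Tc1 | 4/5 = 80% | 26/35 = 74.3% | Yes by time point, no by measure |

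For contrast, take someone who misses only Tb1 but is allowed to continue. That person finishes with 4/5 = 80% of time points, or (35 − 3)/35 = 32/35 = 91.4% of measures, and complies on either count. If removed at Tb1 instead, the same person stays at 40% or 57.1%.

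**4. Effect on the result.** If 24 would have complied and one of them is removed early, the rate is 23/30 = 76.7%, below the goal. With two removed it is 22/30 = 73.3%. Each removal of this kind moves the rate by 1/30 = 3.3 points.

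**5. Chance of reaching the bar.** The documents give no removal rate, so k is assumed. Let k participants be fixed as failures and let the other 30 − k each comply independently with probability p. The chance is P(X ≥ 24), with X ~ Binomial(30 − k, p).

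| p | k = 0 | k = 1 | k = 2 |
|---|---|---|---|
| 0.75 | 0.348 | 0.232 | 0.135 |
| 0.80 | 0.607 | 0.463 | 0.315 |
| 0.90 | 0.974 | 0.936 | 0.858 |
| 0.95 | 0.999 | 0.997 | 0.988 |

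At the compliance the protocol's attrition figure implies (0.75 to 0.80), one removal matters. At 0.90 or above it hardly does.

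**The case against.** The case for leaving the clause alone has real weight.

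- **Rarity.** The protocol calls such withdrawals highly unlikely, and *obviously* points to clear cases, not to one mishandled session. This stands and limits the expected size. It does not justify the clause, because an undefined term leaves the threshold to whoever applies it.
- **Tracking.** Sections 5.4.1 and 5.4.2 already track non-followers and terminations, and section 14.3 already treats participant noncompliance as a deviation. Removals can therefore be reported. But a count of removals cannot show whether those patients would have finished.
- **Timing.** Assessments already completed still count in a listed endpoint, and removal after Tc1 can pass by time point. Someone who does none of the acute-use assessments has at most 2/5 time points or 20/35 measures, and fails whether removed or not. The harm is confined to early or mid-session removal of people who would have reached 75%.
- **Endpoints.** Section 10.1 describes the endpoints as purely recruitment based. The primary objective, two of the five Synopsis endpoints and section 10.3.1 nevertheless include compliance or completion.
- **Sensitivity.** With N = 30 any single dropout near the bar has the same effect. That is true, but this dropout is created by the protocol and can be avoided.

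A reader might also infer that removed participants could be left out of the denominator and inflate the rate: 23 compliers with two others removed would be 23/28 = 82.1% instead of 23/30 = 76.7%. The wording of section 10.3.1, which refers to enrolled participants, does not support that exclusion.

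**Conclusion.** The point holds in a limited form. A stated rule cuts off part of the outcome the study must show, for participants who may be the most informative about feasibility. One early removal of a would-be complier can turn 24/30 (80%) into 23/30 (76.7%). This assumes that true compliance is near the bar, as the 20-25% attrition figure suggests, and that the person removed would have reached 75%. The number of such removals is unknown and expected to be small.

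A reader might infer that staff discretion decides the feasibility result, or that every removal turns partial compliance into full dropout. The documents support neither. The counts of contacts, eligible patients and enrolments cannot be affected, completed assessments are kept, a late removal may still pass, and at underlying compliance of about 90% or more one removal rarely changes the outcome. Nor is the clause worded as a free option: it says such participants would be withdrawn. The discretion lies in the undefined *obviously*.

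**What to change.** Delete reason (1) in section 5.4.1 as a ground for involuntary withdrawal. Record failure to follow instructions as a protocol deviation under section 14.3, with its cause (could not or did not), and keep offering the remaining assessments. Leave the other withdrawal grounds unchanged. Add one sentence to section 10.3.1: a participant the investigator terminates on any remaining ground stays in the denominator, as the reference to enrolled participants already implies, and is reported separately.

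The cost is one clause deleted, a few sentences added, the IRB review that section 13.2 requires for any amendment, and slight extra staff time on participants who would have been removed.

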#### **5.4.2 HANDLING OF PARTICIPANT WITHDRAWALS OR TERMINATION**

All procedures in this study are completely voluntary, and participants may withdraw their consent to participate at any point. Attempts will be made to understand why participants withdraw, as this is important for a feasibility trial, but even in that case giving investigators information concerning withdrawal is voluntary. Termination of participant by investigators, as described above, will also be tracked in case there are procedures that are not feasible for cancer patients to follow. Again, this is critical for a feasibility trial. Once participants withdraw or are terminated, there will be no attempt to follow up with or further engage with the participant.

#### **5.5 PREMATURE TERMINATION OR SUSPENSION OF STUDY (STUDY STOPPING RULES)**

This study may be temporarily suspended or prematurely terminated if there is sufficient reasonable cause. Written notification, documenting the reason for study suspension or termination, will be provided by the suspending or terminating party to the funding agency and regulatory authorities. If the study is prematurely terminated or suspended, the PI will promptly inform the IRB and will provide the reason(s) for the termination or suspension.

Circumstances that may warrant termination or suspension include, but are not limited to:

- Determination of unexpected, significant, or unacceptable risk to participants.
- Insufficient compliance to protocol requirements.
- Data that are not sufficiently complete and/ or evaluable.
- Determination of futility.

### **6 STUDY AGENT**

#### **6.1 STUDY AGENT(S) AND CONTROL DESCRIPTION**

##### **6.1.1 ACQUISITION**

Study staff will not acquire orally administered *Cannabis*. The proposed work will utilize a design that is observational and does not involve assignment by the research team. More specifically, participants who are already planning to try *Cannabis* will choose their own product at baseline and purchase the product at a dispensary. Colorado law requires all edibles to be

tested by a state lab, which allows us to have a precise measure of potency after the participants purchase their products. Importantly, the researchers who conduct the assessments as well as all the senior investigators including the statistician (PI [name]) will be blind to the participant's product choice.

#### **6.1.2 FORMULATION, APPEARANCE, PACKAGING, AND LABELING**

According to Colorado state law, we cannot relabel the packaging of any *Cannabis* product.

#### **6.1.3 DOSING AND ADMINISTRATION**

The patient will use their orally administered *Cannabis ad libitum* at home. This aspect of the design is again consistent with an observational design and differentiates it from a classical interventional clinical trial, which is critically important because it is the only path forward for research on orally administered, legal market *Cannabis* given current federal law. Study staff will not advise participants on or participate in dosing and administration practices.

The disadvantage of our observational design is that we do not have direct control over the choice of product or the dosing and administration of the *Cannabis* product. To address this limitation, we will have participants take and send a picture of their purchased oral cannabis product to our lab via the REDCap system. Colorado requires all strains to be tested by a state licensed lab, and the dispensary that we work with performs cannabinoid and terpene potency testing on each batch produced and sets aside a specific lot of strains corresponding to the ratios utilized in this project (a CBD-dominant strain, a THC-dominant strain, and a THC+CBD strain). Thus, having a picture of the participant's purchased product will allow us to verify the strain and thus, the ratio of cannabinoids contained in the product for a measure of potency to operationalize our user groups.

#### **6.1.4 ROUTE OF ADMINISTRATION**

Oral administration *ad libitum*

#### **6.1.5 STARTING DOSE AND DOSE ESCALATION SCHEDULE**

Starting dose and escalation *ad libitum*

#### **6.1.6 DURATION OF THERAPY**

Two weeks use *ad libitum*

### **7 STUDY PROCEDURES AND SCHEDULE**

#### **7.1 STUDY PROCEDURES/EVALUATIONS**

The complete schedule of measures taken at each assessment are outlined in Table 7.1.

Table 7.1: Schedule of Locations and Assessments			
Timepoint	Measures	Location	Compensation
Baseline (T00)	Pain interference, pain intensity, anxiety symptoms, state and trait anxiety, sleep, quality of life, objective cognition, subjective cognition, demographics, alcohol and substance use history, cancer staging/treatment regimen (EMR)	At home (online)	\$60, 1.5 hours
Two weeks ad libitum use		At home	
Pre-acute Cannabis use (Ta1)	Pain interference, pain intensity, anxiety symptoms, state and trait anxiety, sleep, quality of life, objective cognition, subjective cognition, alcohol and substance use history (timeline follow-back).	At home (online)	
1 hour post-acute Cannabis use (Tb1)	Pain intensity, state anxiety, objective cognition	At home (online)	
2 hour post-acute Cannabis use (Tc1)	Pain intensity, state anxiety, objective cognition	At home (online)	\$100, 2.5 hours
One month follow-up (M1)	Pain interference, pain intensity, anxiety symptoms, state and trait anxiety, sleep, quality of life, subjective cognition, other substance use, Disease status/treatment regimen (EMR)	At home (online)	\$10, 20 minutes

NOTES: EMR=electronic medical record, total compensation possible for 4 hours, 20 minutes of assessment=\$170

## 7.2 LABORATORY PROCEDURES/EVALUATIONS

The complete list of measures and procedures is detailed in Table 7.2 below.

Table 7.2: Study Measures	
Domain	Measure
Pain interference	REDCap: Promis Pain Interference CAT
Pain intensity	REDCap: Pain Intensity
Anxiety symptoms	Beck Anxiety Inventory (BAI)

State and trait anxiety	State-Trait Anxiety Inventory (STAI)
Sleep	Pittsburgh Sleep Quality Index (PSQI)
Quality of life	Functional Assessment of Cancer Therapy - General (FACT-G)
Objective cognition	Telephone Interview for Cognitive Status (TICS) Neurocognitive battery targeting executive function*
Subjective cognition	Functional Assessment of Cancer Therapy – Cognitive Function (FACT-Cog)
Substance Use History	Marijuana Consumption Questionnaire (MCQ) Alcohol Use Disorder Identification Test (AUDIT) Timeline Follow-Back (TLFB)

\*Tests for which deficits have been observed previously among cancer patients  and include measures that are recommended by the International Cancer and Cognition Task Force

### 7.2.1 CLINICAL LABORATORY EVALUATIONS (RESEARCH PROCEDURES)

Pregnancy screening. A urine pregnancy screening test will be administered to all female potential study participants of child-bearing age after informed consent has been obtained at the Baseline visit to verify eligibility for the study. For the pregnancy screening, a trained research assistant will deliver a urine receptacle to the participant's home. The participant will then use the restroom in their home and return the receptacle to the research assistant to complete the urine test in the mobile laboratory.

### 7.2.2 OTHER ASSAYS OR PROCEDURES (RESEARCH)

**Pain Intensity and Pain interference.** We employ two self-report measures of pain intensity and interference. Pain Intensity consists of one item asking about the participant's level of pain in the past seven days. Participants are asked to rate their pain on a scale from 0 (no pain) to 10 (worst imaginable pain). The Promis Pain Interference CAT asks participants about how their experience of pain interfered with or affected their enjoyment of various daily activities in the past seven days. The scale is computer-adapted and has a minimum of four questions and a maximum of 12 questions.

**Anxiety and Mood Disturbance.** The primary measure of lasting effects of *Cannabis* anxiety, the Beck Anxiety Inventory (BAI) consists of 21 items, each describing a symptom of anxiety. Secondary assessments of anxiety and mood disturbance include the Positive and Negative Affect Schedule (PANAS), a brief, reliable and valid measure of positive and negative affect and the Beck Depression Inventory-II (BDI-II) consisting of 21 scaled statements designed to assess symptoms of depression. As its name suggests, the State-Trait Anxiety Inventory (STAI) assesses both trait and state anxiety.

**Sleep.** Perceived sleep quality will be assessed by the commonly-used and well-validated Pittsburgh Sleep Quality Index.

**Quality of Life.** A commonly-used quality of life measure specific to cancer patients will be used to assess perceived quality of life: the Functional Assessment of Cancer Therapy - General

(FACT-G) assesses aspects of quality of life specific to cancer patients, including physical (e.g., nausea, lack of energy), social, emotional, and cognitive well-being.

**Objective and Subjective Cognitive Functioning.** The Telephone Interview for Cognitive Status (TICS) will be used at screening to assess for moderate to severe cognitive impairment that would preclude enrollment as a study participant. The TICS is a widely used and validated measure of cognitive impairment that is highly correlated to the Mini Mental State Exam (MMSE) . To assess objective cognitive functioning, we will conduct a neurocognitive battery on all participants that targets executive function. We will conduct this battery using Tatool, an open-source software developed to run psychological experimental studies. This battery includes tests for which deficits have been observed among cancer patients and include measures that are recommended by the International Cancer and Cognition Task Force. The battery covers the domains found to be sensitive to the effects of *Cannabis*. Specifically, the cognitive battery will include the Stroop Task to assess inhibition and the Shape/Color Shifting Task to assess shifting. We will assess subjective cognitive functioning with the Functional Assessment of Cancer Therapy – Cognitive Function (FACT-Cog), a reliable and valid assessment of perceived cognitive functioning specifically designed for cancer patients.

**Health/Disease Status and Treatment Regimen.** With the assistance of our oncology collaborators and OCRS staff, and with explicit informed consent from our patient participants, we will access Electronic Medical Records (EMRs) via the Health Data Compass coinciding with the Baseline encounter and the One Month Follow-up. We will obtain data regarding cancer staging, tumor characteristics, treatment regimen (observation versus chemotherapy, targeted therapy, immunotherapy, combination of therapies, or other), current medications and doses (including treatment-supporting medications only), and any co-existing conditions.

**Substance Use History.** The Marijuana Consumption Questionnaire (MCQ) is used to collect information on the frequency and quantity of cannabis use, age of first use, peer use, perceived risk from *Cannabis*, and perceived availability of *Cannabis*. The Alcohol Use Disorder Identification Test (AUDIT) will be used to examine the extent of alcohol use and problems related to alcohol use. A Timeline Follow-Back (TLFB) will be used to assess daily substance use for the 30 days prior to the baseline session and for the 14 days prior to the 2-week pre-acute use session. The TLFB is a calendar assisted structured interview that provides a study participant with temporal cues to increase the accuracy of recall. This instrument has demonstrated test-retest reliability and validity

**Demographics.** Personal information including gender, age, detailed race/ethnicity, and SES will be collected by self-report in addition to extraction from the EMR obtained via Health Data Compass.

**Pregnancy Screening.** A urine pregnancy screening test will be administered to all female potential study participants of child-bearing age after informed consent has been obtained at the Baseline visit to verify eligibility for the study. For the pregnancy screening, a trained research assistant will deliver a urine receptacle to the participant's home. The participant will then use the restroom in their home and return the receptacle to the research assistant to complete the urine test in the mobile laboratory.

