### 4.1 DESCRIPTION OF THE STUDY DESIGN

Tightly controlled experimental laboratory studies (e.g., clinical trials with randomization) using *Cannabis* products available in state-regulated markets are simply, at this point, not possible owing largely to federal law and the University requirements related to the Controlled Substances Act and Drug Free Schools and Communities Act. Because a traditional clinical trial design is not possible given the current federal status of *Cannabis* products, we will use a patient-oriented, prospective observational design. Specifically, individuals who have already decided to try *Cannabis* for their cancer treatment-related symptoms will initiate use of an orally administered product they have selected. A research assistant will provide information on the range of edible cannabis products and basic information about their various cannabinoid profiles, approximate prices, and nearby locations where participants may choose to purchase their product. The participants will then purchase the product and decide how often and how much to use. This approach is consistent with federal law and supported by our preliminary and ongoing studies (1R01AT009541-01, 1R01DA044131-01, CDPHE2902, R01DA039707). Participants will take the product as they see fit, without any frequency or dosing instructions from study staff, for two weeks, at which time they will be scheduled for their Pre- and Post- Administration Assessment (Ta1-Tc1) so that we may examine the acute effects of the product. The final follow-up will be one month later via an online survey sent directly to the participant via email. Details about the various study sessions are provided in Section 7.

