### 7.3.2 ENROLLMENT/BASELINE

Potential participants who meet inclusion criteria will be scheduled for a baseline session. A trained research assistant will meet remotely with the participant via phone or Zoom. Each participant will go through the informed consent process. Once consented, participants will complete current and historical health and substance use assessments and cognitive testing (see Table 7.1). Participants will complete assessments via emailed, individually tailored links hosted by and integrated into the study's REDCap databases (<https://redcap.ucdenver.edu/>). Participants will then receive a consultation from research staff on the range of edible *Cannabis* products and basic information about their various cannabinoid profiles, approximate prices, and nearby locations where participants may choose to purchase their product. Again, research staff will not advise study participants to purchase any specific product. Participants will be compensated with a \$60 grocery store gift card for their time and effort at the end of the visit, which will be mailed to their home.

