**Pre- and Post- Administration Assessment (Ta1-Tc1).** The Pre- and Post- Administration Assessment will take place two weeks (+/- 4 days) following the baseline session. A trained research assistant will meet remotely with the participant via phone or Zoom. Links to assessments will be emailed to the participant at the start of the session. Prior to taking their *Cannabis*, participants will complete self-report assessments, including those assessing quantity/frequency of *Cannabis* use and symptom severity over the prior two weeks (Ta1). They will then consume their orally administered *Cannabis*. Because 60 minutes is the average time that CBD and THC levels begin to peak in the blood after oral administration of *Cannabis* extract, assessments of the acute effects of *Cannabis* (see Table 7.2) will begin one hour (+/- 5 minutes) post-edible consumption (Tb1). After peak, levels steadily decrease over the next 2-3 hours and by 4 hours post-ingestion begin to rapidly drop off in blood. To account for individual differences in metabolism and sensitivity, participants will be assessed again at 2 hours (+/- 5 minutes) post-consumption (Tc1). After completing the 1- and 2- hour post-consumption assessments, participants will receive a \$100 grocery store gift card as compensation for their time and effort, which will be mailed to their home.

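### Does the fixed 14-day substance-use look-back at the two-week session lose product-use data that the study needs?

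*Combined protocol and SAP*

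**What the plan says.** Section 7.2.2 (Substance Use History) describes two TLFB periods: one "for the 30 days prior to the baseline session", and one "for the 14 days prior to the 2-week pre-acute use session". Section 7.3.3 gives the timing of the second session, which "will take place two weeks (+/- 4 days) following the baseline session".

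On product use, Section 4.1 says that participants "will initiate use of an orally administered product they have selected" and take it as they see fit "for two weeks, at which time they will be scheduled for their Pre- and Post- Administration Assessment". Section 6.1.1 says that they "will choose their own product at baseline and purchase the product at a dispensary", and Section 7.3.2 has staff inform them at baseline about "nearby locations where participants may choose to purchase their product". Purchase therefore comes after the baseline consultation, at a time the plan does not fix.

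The product photograph (Sections 6.1.3 and 7.3.3) and the REDCap selection report (Section 10.5.1) are described as ways to learn which product was chosen. Neither is described as recording when use began.

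**The concern.** A fixed look-back attached to a visit with a window of plus or minus 4 days cannot equal the interval since baseline for every participant. When the session is late, the days that drop out are the first ones after baseline, which is when use of the new product may begin.

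The plan speaks of two weeks of use, but the session is timed from baseline and not from the first dose taken. Without a first-use date, time on product at the two-week session is not directly known. In an observational study where participants choose product, amount and frequency, the TLFB is the only daily record of use described. If exposure fed an analysis, a gap at the start of exposure and an unknown start date would both matter.

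**Working it through.** **Inputs.** Session day s = 14 ± 4, so s runs from 10 to 18 (Section 7.3.3). Look-back at that session: 14 days; at baseline: 30 days (Section 7.2.2). Days from baseline to first use, d: not in the documents, so it is varied below. How often s takes each value is not given either, so no expected loss can be calculated.

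**Coverage.** With baseline as day 0, the baseline TLFB covers days −30 to −1 and the second covers days s−14 to s−1.

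- Days repeated from the baseline TLFB = max(0, 14 − s)
- Post-baseline days in neither period = max(0, s − 14)
- Share of the interval covered = min(14, s)/s

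| Session day s | Days repeated | Days in neither | Share of interval covered |
|---|---|---|---|
| 10 | 4 | 0 | 100% |
| 11 | 3 | 0 | 100% |
| 12 | 2 | 0 | 100% |
| 13 | 1 | 0 | 100% |
| 14 | 0 | 0 | 100% |
| 15 | 0 | 1 | 14/15 = 93.3% |
| 16 | 0 | 2 | 14/16 = 87.5% |
| 17 | 0 | 3 | 14/17 = 82.4% |
| 18 | 0 | 4 | 14/18 = 77.8% |

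**Days of use that could be lost.** An uncovered day matters for exposure only if the product was used on it. The most that can be lost is max(0, s − 14 − d). It is an upper bound because participants need not use the product every day.

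| d | s = 15 | s = 16 | s = 17 | s = 18 |
|---|---|---|---|---|
| 0 | 1 | 2 | 3 | 4 |
| 1 | 0 | 1 | 2 | 3 |
| 2 | 0 | 0 | 1 | 2 |
| 3 | 0 | 0 | 0 | 1 |
| 4 or more | 0 | 0 | 0 | 0 |

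**Elapsed time since first use at the session** is s − d: 9 to 17 days if d = 1, and 6 to 14 days if d = 4. This is calendar time, not a count of days of use. The two weeks in Sections 4.1 and 6.1.6 are a nominal period, and Section 7.3.3 supplies the working visit window. These statements fit together and need no reconciliation.

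**What uses these data.** The Synopsis endpoints count contacts, eligible and enrolled patients, completed assessments and completers. Section 10.1 says the endpoints concern recruitment only and adds completeness checks and summary statistics. Section 10.3.1 defines reasonable compliance as 75% of assessments completed, with 80% retention as the goal. A TLFB counts as one completed assessment whatever its look-back. None of these results depends on d, or on whether the look-back starts at baseline.

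**The case for a change.** The strongest case for a change is that it would be cheap and would suit the purpose of a pilot. Running the second TLFB from the baseline date removes both gap and overlap on every permitted day. A fixed 14-day window could still be rebuilt by joining it to the baseline TLFB. One REDCap field would capture first use. Section 10.4 says the pilot should show which procedures need changing before a full study, and Section 6.1.3 concedes that the investigators do not control dosing.

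Part of this stands. The day counts are right. For someone already using cannabis, a TLFB that is not described as product-specific would not cleanly show when the chosen product was started. Such people can enrol: Section 5.1 asks only for intent to use, the drug exclusion in Section 5.2 concerns other drugs, and Section 7.3.3 refers to participants who are not new to cannabis.

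It does not amount to a needed correction. For people new to cannabis, a daily calendar normally dates first use unless it falls in the short gap. Starting the look-back at baseline replaces an equal 14-day recall with one of 10 to 18 days, so summaries need per-day rates and late attenders must recall up to 4 more days. A first-use field would serve no planned analysis. Nor does silence in the protocol show that the field is absent from the case report forms or procedures manual, which it mentions but does not reproduce.

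**Conclusion.** No change is called for. The mismatch leaves at most 4 post-baseline days in neither TLFB period, and losing 4 days of use requires a session on day 18, first use on the baseline day and use on each of those days. The loss is zero for sessions by day 14 or when first use comes 4 or more days after baseline. Elapsed time since first use is uncertain mainly for people already using cannabis. Only descriptive exposure data are touched; recruitment, retention and compliance results stay the same.

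This rests on the endpoints remaining as stated in the Synopsis and Section 10.1. A later study that analysed exposure would have reason to revisit both points. In this pilot, an analyst can report the actual session day and summarise TLFB use per day observed.

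Two neighbouring points are clerical or missing detail. The abbreviation MCQ stands for a consumption questionnaire in Table 7.2 and Section 7.2.2, but for a craving questionnaire in the abbreviation list, the Table 7.3 footnote and reference 96. No look-back is stated for the TLFB at the one-month follow-up, although Section 7.3.4 says the survey there asks about the past month. The marks in Table 7.3 are too damaged in the extracted text to support any claim about when the MCQ is given.
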